5. DEMOGRAPHIC AND OTHER BASELINE CHARACTERISTICS

5.1. Demographics and Baseline Characteristics

Demographic variables include age, sex, race, and ethnicity. Baseline characteristics include American Society of Anesthesiologists (ASA) physical status, previous opioid history (Y/N), height, weight (kg) and BMI (kg/m²). Demographics and baseline characteristics will be presented in by-patient listings and summarized.

5.2. Medical History

Medical history, as collected at screening and prior to surgery, will be presented in a by-patient listing and summarized by body system.

5.3. **Prior and Concomitant Medications**

Prior and concomitant medications are collected at screening and updated throughout the study as needed. Prior and concomitant medications will be coded using WHODDE (C Format) version 01SEP2017. The number and percentage of patients who take concomitant medications will be summarized by drug class (Anatomical Therapeutic Chemical (ATC) Level 3) and PT for the safety population and presented in a by-patient listing.

Prior medications, including medications given during surgery, and non-medical therapies will appear in a data listing but will not be summarized.

Medications will be classified as follows:

- Prior medications. Prior medications/therapies are those that have a start date/time and end date/time prior to the start of the first treatment administration. Prior medications will not be tabulated but will be included in the data listings.
- Concomitant medications. Medications will be considered as concomitant if the medication is taken on or after the date/time of first intake of treatment product and has a start date/time that is no later than 1 day (24 hours) after the start of the last administration of study medication.
- New-onset concomitant medications are defined as those medications starting between the start of the first dose of study medication and 1 day (24 hours) after the start of the last dose of study medication. Medications with no start time but starting on the day of study medication will be assumed to be new-onset.
- Post-treatment medications. Post-treatment medications are defined as a medication with a start date/time at least 24 hours (1 day) after the start of the last dose of study medication.

If a missing medication start date cannot be definitively determined as having started after first dose, the medication will be considered as started prior to first dose; similarly, if a missing medication stop date/time cannot be determined as having stopped prior to first dose, the medication will be considered concomitant (taken after first dose). Imputation of missing start CONFIDENTIAL

and stop date/times will be performed in the same manner as described for AEs in Table 2. Medications with entirely missing start and stop dates will be listed but not included in the tabulations.

6. MEASUREMENTS OF TREATMENT EXPOSURE

Patient dosing data will be listed and the number of doses per subject and total exposure (mg) per subject will be tabulated. If less than the complete volume of study medication is infused, total exposure will be calculated as the intended dosage (50mg) times the proportion of total saline volume infused (xx mL / 50 mL).

- The duration of exposure will be defined in hours, in which the time from the start of the first dose to start of the last dose, plus 4 hours (i.e., exposure is assumed to be 4 hours for each dose), will be tabulated.
- The number (%) of patients by number of doses received will be presented. The maximum total number of doses is 43.
- The total exposure (mg) will be summarized through 24, 48, 72, 96, 120, 144 and 164 hours, respectively. Maximum exposure is 2150 mg (given at Hours 0, 2, 4, and then 4 hours up to 164).
- If infusion end time is not available, the end time will be imputed as 15 minutes after the infusion start time for use in calculations dependent upon the end time.

In addition, cumulative percent of subjects (%) versus total study drug exposure will be provided graphically.

Tramadol Infusion 07FEB2019

7. OVERVIEW OF ANALYSIS ISSUES

No inferential testing is planned for this safety-based single arm study.

7.1. Handling of Dropouts or Missing Data

No study outcomes will be imputed.

7.2. Assessment Time Windows

Summaries will be based on the nominal protocol-specified visits as appropriate.

8. EFFICACY EVALUATION

The primary objective of this study is to evaluate the safety of AVE-901. Efficacy is considered a secondary, exploratory, given that this is an uncontrolled study in patients with various surgery types. Efficacy will be assessed by patient global assessments (PGAs) using a 5-point scale.

8.1. Efficacy Outcome

Patient Global Assessment of efficacy will be collected at 24 hours post first dose and EOT. The question to be posed is "How would you rate the study medication in terms of its effectiveness in controlling your pain?" (0=poor; 1=fair; 2=good; 3=very good; 4=excellent). If the patient continues treatment beyond Hour 24, PGA will be conducted at Hour 24 and EOT (total of 2 PGAs). If the patient ends treatment prior to Hour 24, PGA will be conducted as part of the EOT visit (total of 1 PGA).

The PGA results will be presented in a summary table by time point. The number (%) of subjects answering in each category will also be presented by time point.

Individual PGA scores will be listed

9. SAFETY EVALUATION

9.1. Overview of Safety Analysis Methods

The safety analysis will be descriptive in nature. All safety data will be listed, and data will be tabulated where the data warrant. Safety data include:

- AEs, including assessment of infusion site local reactions (skin and vein)
- Clinical laboratory tests (hematology panel, chemistry panel and urinalysis) pretreatment and discharge
- Vital signs including: respiratory rate, heart rate, oral temperature, pulse oximetry (SpO2) and BP, as per the schedule of events
- PE at pre-treatment and discharge
- 12-lead ECG at protocol specified time points
- Concomitant treatments

Anti-emetic usage data will be included with the concomitant treatments. Exploratory analyses of use of anti-emetics may be performed if warranted. Other safety data presentations will be descriptive in nature and no formal statistical tests will be performed.

ECG results will be analyzed on an ongoing basis by a central ECG reader on an individual patient level.

9.2. Adverse Events

Any events starting before the first dose of treatment will be reported as Medical History. Verbatim terms used by investigators to identify AEs in the CRFs will be mapped to the appropriate PT and SOC using a standardized coding dictionary (MedDRA Version 20.1). All coding will be reviewed prior to database lock. All recorded AEs will be listed; adverse events starting on or after the first dose of treatment are considered treatment-emergent adverse events as per the protocol, but the definition of treatment emergent will be further categorized for summaries as follows:

- Adverse events occurring on or after the first dose of study medication, and within 1 day (up to 24 hours) after the start of the last dose of study medication. For simplicity, these will be referred to as Treatment Emergent AEs (TEAEs) in the summaries.
- Events occurring after that will be presented as Post-Treatment AEs.

Separate tabulations will be presented for TEAEs and for Post-Treatment AEs.

For evaluation of causal relatedness to treatment, the categories are definite, probable, possible, remote or definitely not. For categorization in the summary tables, AEs designated as definite, probable, or possible will be considered to be related.

For the evaluation of event severity, the criteria are based on National Cancer Institute Common

CTC Grade	CTCAE Grade Description
Grade 1: Mild	Asymptomatic or mild symptoms; clinical or diagnostic observations only; intervention not indicated.
Grade 2: Moderate	Minimal, local or noninvasive intervention indicated; limiting age- appropriate instrumental ADL^1 .
Grade 3: Severe	Severe or medically significant but not immediately life- threatening; hospitalization or prolongation of hospitalization indicated; disabling; limiting self-care ADL ² .
Grade 4: Life-threatening	Life-threatening consequences; urgent intervention indicated.
Grade 5: Death	Death related to the AE.

Terminology Criteria for Adverse Events (NCI-CTCAE), Version 4.03:

¹ ADL = Activities of Daily Living. Instrumental ADL refer to preparing meals, shopping for groceries or clothes, using the telephone, managing money, etc.

² Self-care ADL refer to bathing, dressing and undressing, feeding self, using the toilet, taking medications, and not bedridden.

Local tolerability at the infusion site will be assessed for pain, swelling, tenderness, and erythema. Any such AEs related to tolerability at the infusion site will be identified by the sponsor and medical monitor for listing and possible summarization.

In addition to a listing of all TEAEs, treatment related TEAEs, serious TEAEs, TEAEs leading to premature discontinuation from the study, and TEAEs related to local tolerability at the infusion site will be provided.

An overall summary will be prepared including both the number of TEAEs, and the number of patients with TEAEs, as well as SAEs, treatment related TEAEs, TEAEs by severity and TEAEs leading to premature discontinuation from study.

Incidence of TEAEs will be summarized by SOC and PT sorted in descending frequency by SOC, and then by PT within SOC. These summaries will be given in separate tables for each of the following TEAE event sets:

- All events (Post-Treatment AEs will be tabulated separately)
- Treatment related events (defined by a relationship to study drug of possible, probable, or definite). (Post-Treatment AEs will be tabulated separately)
- Events leading to premature discontinuation from study
- Events related to local tolerability at the infusion site
- Events by maximum severity

If a given patient experiences a TEAE that maps to the same PT more than once, the patient will be counted once for the PT at its greatest severity (i.e., mild, moderate, or severe) and causality

Tramadol Infusion 07FEB2019

(i.e., attribution to study material).

TEAEs occurring within 1 hour of any infusion will be summarized.

The number/ percentages of subjects with any TEAE will also be presented by Infusion #. Each AE will be matched to an Infusion # by the start date/time of the AE (after all imputation for missing dates). E.g., An AE with start date/time on or after the start date/time of Infusion #3 and prior to start date/time of Infusion #4, will be counted under Infusion #3. Percentages will be calculated from the number of subjects receiving the referenced injection (i.e., Subjects receiving 4 injections will be counted in the denominator for Infusion #1, #2, #3 and #4, and will not be included in the denominator for other Infusions).

Duration of a TEAE will be computed in days as the stop date of the event minus the start date plus 1. If reported as ongoing at the time of database lock, the duration of the AE will be calculated using the date/time of the last visit or the last date of any adverse event for the patient in the database, whichever is later. If a TEAE is considered resolved, but the stop date is missing, the last day of the month will be imputed if the month and year are available. If only the year is available, and the year is the same as the year of the last visit, the stop date will be imputed as the latest of the last visit date or latest event for the patient in the database. If the year of the event is prior to the year of the last treatment, the end day and month will be imputed as 31 December.

For missing or partial start dates, they will be imputed as temporally related to the first dose of study medication. Table 2 demonstrates the rules to be used to impute any missing AE start dates.

Missing Start Date Portion	Prior to Treatment	Same as Treatment Start Date	After Treatment Start Date
Day	Month and Year < Month and Year of first treatment:	Month and Year = Month and Year of first treatment:	Month and Year > Month and Year of First Treatment:
	Start Day = 1	Start Day = Day of	Start Day = 1
	Stop Day = last day of the month	first treatment Stop Day= last day of the month	Stop Day= last day of the month
Day and Month Define Day as above, then:	Year < Year of first treatment:	Year = Year of first treatment:	Year > Year of first treatment:
	Start Month = July	Start Month =	Month = January
	Stop Month = Dec	Month of first treatment	Stop Month = Dec
		Stop Month = Dec	
Day, Month, and Year	To be conservative, completely missing start dates will be set to the date of first treatment, completely missing end dates will be set to the date of last contact.		
Time	Missing start times will b dose administration if AE administration)		r the start time of the first of first dose
	Missing stop times will b	e imputed as 23:59	

Table 2:Table of Imputation Rules for Missing AE Start Date Times (Study AVE-
901-104)

After following these imputation rules, if the start date/time is imputed as a date after the end date/time, the start date/time will be set to the end date/time to provide a positive duration for the event incidence.

Missing assessments for AE study medication relationship or severity will be analyzed as related or severe respectively. No other imputation is planned for safety data.

9.2.1. Subgroups

Descriptive analysis of treatment-emergent AEs (TEAEs), serious adverse events (SAEs), and discontinuations due to AEs, will be provided by the following subgroups:

- Gender (male versus female)
- Race (White versus non-White)
- Age (using the study median age: less or equal to (≤) median age group versus greater than (>) median age group)
- Age (<65 vs >=65 years)
- BMI (> versus <= median value)
- Surgery Type (Orthopedic versus soft tissue)

9.3. Deaths and Serious Adverse Events

A serious adverse event is an AE occurring during the study that fulfills one or more of the following:

- Results in death
- It is immediately life-threatening
- It requires in-patient hospitalization or prolongation of existing hospitalization
- It results in persistent or significant disability or incapacity
- Results in a congenital abnormality or birth defect
- It is an important medical event that may jeopardize the patient or may require medical intervention to prevent one of the outcomes listed above

Serious adverse events and deaths will be listed and summarized separately for the safety population.

9.4. Clinical Laboratory Evaluation

Clinical laboratory test results (blood chemistry, hematology and urinalysis) will be listed for individual patients. Baseline for clinical laboratory parameters will be defined as the last evaluation before dosing with study treatment. For each individual lab test value, results and change from baseline will be summarized by time point (baseline and at discharge).

The number and percent of patients with potentially clinically significant (PCS) values will be summarized. Only new-onset PCS values, i.e., patients with pre-existing PCS values at pre-treatment will not be considered to have new-onset values on-treatment. The criteria used to identify potentially clinically significant laboratory values are listed in Table 3.

Variable Name (Normal Range)	Low	High
Hematology		
White Blood Cells (NR: 3.7 - 11.0x K/cu /mm)	$\leq 2.8 \text{ x } 10^3 \text{ /mm}^3$	$\geq 16 \text{ x } 10^3 \text{ /mm}^3$
Neutrophils (NR: 46 - 72%)	$\leq 15\%$	NA
Lymphocytes (NR: 14 - 46%)	NA	≥75%
Monocytes (NR: 0 - 11%)	NA	≥15%
Eosinophils (NR: 0 - 7%)	NA	≥10%
Basophils (NR: 0 - 3%)	NA	≥10%
Red Blood Cells Female: (NR: 3.8 - 5.1 x 10 ⁶ /mm ³) Male: (NR: 4.1 - 5.6 x 10 ⁶ /mm ³)	≤3 x 10 ⁶ /mm ³ ≤3.5 x 10 ⁶ /mm ³	$\geq 6 \ge 10^6 / \text{mm}^3$ $\geq 6.5 \ge 10^6 / \text{mm}^3$
Hematocrit		
Female: (NR: 36.4 – 48.9%)	≤32%	NA
Male: (NR: 41.6 – 54.1%)	≤37%	NA
Hemoglobin Female: (NR: 11.5 – 16.0 g/dL) Male: (NR: 13.0 – 17.5 g/dL)	≤9.5 g/dL ≤11.5 g/dL	NA NA
Platelets (NR: 125 - 375 K/cu /mm)	$\leq 75 \text{ x } 10^3 \text{ /mm}^3$	\geq 700 x 10 ³ /mm ³
Serum Chemistry		
Total protein (NR: 6.0 - 8.0 g/dL)	≤4.0 g/dL	≥10 g/dL
Albumin (NR: 3.5 - 5.5 g/dL)	≤2.0 g/dL	NA
Creatinine (NR: 0.7 - 1.4 mg/dL)	NA	$\geq 2 \text{ mg/dL}$
BUN (NR: 5 - 20 mg/dL)	NA	\geq 30 mg/dL
Uric Acid: (NR: 2.0 - 6.0 mg/dL	NA	≥9.0 mg/dL
Bilirubin total (NR: 0.1 – 1.1 mg/dL)	NA	$\geq 2.5 \text{ mg/dL}$
Bilirubin direct (NR: 0 - 0.4 mg/dL)	NA	≥0.6 mg/dL
Alkaline phosphatase (NR: 30 - 115 U/L)	NA	≥390 IU/L
AST/SGOT	NA	□150 U/L
ALT/SGPT	NA	□165 U/L
CPK (NR: 24 - 169 U/L)	NA	≥702 IU/L
Glucose random (NR: 60 - 115 mg/dL)	≤40 mg/dL	\geq 250 mg/dL
Calcium (NR: 8.5 - 10.5 mg/dL)	≤8.0 mg/dL	≥12 mg/dL

Table 3:List of Potentially Clinically Significant Ranges for Clinical Laboratory
Parameters (Study AVE-901-104)

Variable Name (Normal Range)	Low	High
Phosphorous (NR: 2.5 - 4.5 mg/dL)	\leq 1.7 mg/dL	NA
Sodium (NR: 133 - 145 mEq/L)	$\leq 126 \text{ mEq/L}$	$\geq 156 \text{ mEq/L}$
Potassium (NR: 3.5 - 5.0 mEq/L)	≤3 mEq/	≥6 mEq/L
Chloride (NR: 95 - 110 mEq/L)	≤90 mEq/L	$\geq 118 \text{ mEq/L}$
Bicarbonate (CO ₂) (NR: 21 - 33 mEq/L)	$\leq 19 \text{ mEq/L}$	\geq 35 mEq/L
Urinalysis		
Specific gravity (NR: 1.002 - 1.035)	≤1.001	NA
pH (NR: 5.0 – 8.0)	≤4	≥9
UA Ketones (Normal = negative) mg/dL	NA	$\geq 2+$
UA Protein (Normal = negative) mg/dL	NA	$\geq 2+$
UA Blood (Normal = negative)	NA	\geq 3+
UA Leukocyte Esterase	NA	\geq 3+
Nitrates	NA	≥2

Each clinical laboratory test will be defined to be "Low", "Normal", or "High", according to the normal reference range from the clinical laboratory. The number and percentage of patients who have a shift from within to outside the normal reference range from baseline (and vice versa) to each follow-up visit will be summarized by time point.

9.5. Vital Signs

Vital signs results including BP (systolic and diastolic), heart rate, respiration rate, pulse oximetry, and temperature will be listed for individual patients. Baseline for vital signs measurements will be defined as the last evaluation before dosing with study medication. Vital signs and changes from baseline will be summarized by time point.

Vital sign parameter outcomes will be assessed for potential clinical significance; observed values and changes from pre-treatment to on-treatment time points will be tabulated for continuous parameters, as warranted.

The number and percent of patients with potentially clinically significant (PCS) values during the treatment phase will be summarized. A focus will be on new-onset PCS values, i.e., patients with pre-existing PCS values at pre-treatment will not be considered to have new-onset values on-treatment. The criteria for identifying potentially clinically significant vital signs values are provided in Table 4.

Table 4:List of Potentially Clinically Significant Ranges for Vital Sign Parameters
(Study AVE-901-104)

Variable Name	LOW	HIGH

Systolic BP	<86 mm Hg OR a decrease of ≥25 mm Hg from baseline	>200 mm Hg OR an increase of ≥25 mm Hg from baseline
Diastolic BP	<48 mm Hg OR a decrease of ≥20 mm Hg from baseline	>110 mm Hg OR an increase of ≥20 mm Hg from baseline
Heart rate ¹	1) <45 bpm OR a decrease of ≥25 bpm from baseline	1) >105 bpm and increase ≥25 bpm from baseline OR >125 bpm

¹ bpm: beats per minute

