3. GENERAL ANALYSIS AND REPORTING CONVENTIONS

This section discusses general policies to be employed in the analysis and reporting of the data from the study. Departures from these general policies are provided in the specific detailed sections of this SAP. When this situation occurs, the rules set forth in the specific section take precedence over the general policies.

All continuous study assessments will be summarized by time point (as applicable) using the descriptive statistics n, mean, SD, median, and range (minimum, and maximum). All of the categorical study assessments will be summarized by time point (as applicable) using frequency counts and rates of occurrence (%).

The treatment group will be labeled as '**Tramadol 50 mg**' for all outputs. All study data will be listed by study center, patient, and time point (as applicable).

No preliminary rounding will be performed; rounding will only occur after the analysis. To round, consider the digit to the right of the last significant digit: if <5, then round down; if \geq 5, then round up. Means and medians will be presented with one more decimal place than the precision of the raw data. Standard deviations will be presented with two more decimal places than the precision of the raw data. Percentages will be presented with one decimal place. Minimums and maximums will be presented with the same precision as the original data.

All analyses will be performed using the SAS System® version 9.3 or higher. The domain (Study data tabulation Model [SDTM]) and analysis (Analysis Data Model [ADaM]) data sets will be taken as input to the SAS programs that generate the report-ready tables, figures and listings. The submission ready SDTM and ADaM data sets will be provided to the sponsor along with display deliveries.

The following conventions will be used throughout the study analysis:

- Time T0 is the time of start of the first study drug administration.
- Study Day is defined as (Date of Assessment minus Date of First Dose of Study Medication). The first day of dosing is Study Day 0. The day immediately prior to first dose is Study Day -1. Study Day will be calculated for every record in the database and presented alongside the date fields in the data listings, where applicable. For instance, the start *date* of each TEAE will also have the Start *Day* presented in the listings.
- Assessment and visit times are defined relative to time T0.

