9.7. ECG Examinations

ECG examination interpretation results and heart rate and interval duration results will be listed for individual patients. Baseline for ECG continuous measurements will be defined as the last evaluation before dosing with study medication. Continuous ECG values and changes from baseline will be summarized by time point. The proportion of subjects with Normal, Abnormal: Not Clinically Significant, and Abnormal: Clinically Significant will be summarized by time point.

The ECG analysis will include a careful review of QTcF values. As part of this review, a summary of the number (percent) of patients with QTcF values in the following ranges will be provided: \leq 450 msec, >450 to \leq 480 msec, >480 to \leq 500 msec, and >500 msec. This will be performed by visit as well as at ANY time during the treatment period (where the highest QTcF value will be used for that assessment).

The incidence of PCS values will be presented, with a focus on new-onset PCS values. The criteria for identifying potentially clinically significant ECG values are provided in Table 5.

Table 5:List of Potentially Clinically Significant Ranges for ECG Parameters (Study
AVE-901-104)

PR Interval	
High: >200 msec OR Increase ≥ 20 msec from baseline	
QRS Interval	
High: >100 msec OR Increase ≥ 10 msec from baseline	
QT Interval	
High: >500 msec OR Increase ≥ 60 msec from baseline	
QTcF Interval	

High: > 450 msec (Males); >470 msec (Females) OR Increase \geq 50 msec from baseline	;
--	---

Heart Rate

Low: <45 bpm OR a decrease of \geq 25 bpm from baseline

High: >105 bpm and increase \geq 25 bpm from baseline OR >125 bpm

Tramadol Infusion 07FEB2019

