Table 14.3.1.8.1	Incidence of Serious Adverse Events by System Organ Class, Preferred Term and Surgery Type	Safety Population	Surgery Type		Repeat
Table 14.3.1.8.2	Incidence of Serious Adverse Events by System Organ Class, Preferred Term and Gender	Safety Population	Gender		Repeat
Table 14.3.1.8.3	Incidence of Serious Adverse Events by System Organ Class, Preferred Term and Race	Safety Population	Race		Repeat
Table 14.3.1.8.4.1	Incidence of Serious Adverse Events by System Organ Class, Preferred Term and Age Group (Median)	Safety Population	Age (<=, > Median)		Repeat
Table 14.3.1.8.4.2	Incidence of Serious Adverse Events by System Organ Class, Preferred Term and Age Group (65 Years Old)	Safety Population	Age (<65, >= 65 years old)		Repeat
Table 14.3.1.8.5	Incidence of Serious Adverse Events by System Organ Class, Preferred Term and BMI	Safety Population	BMI		Repeat

CONFIDENTIAL

Page 39 of 43

Protocol AVE-901-104 Phase 3 Open-Label Avenue Therapeutics, Inc.

Tramadol Infusion 07FEB2019

	Shift from Baseline to End of Treatment in Serum Chemistry Parameters	Safety Population	Repeat
	Potentially Clinically Significant Results in Chemistry values	Safety Population	Unique
	Hematology Laboratory Parameters: Results and Change from Baseline to End of Treatment	Safety Population	Repeat
	Shift from Baseline to End of Treatment in Hematology Parameters	Safety Population	Repeat
	Potentially Clinically Significant Results in Hematology values	Safety Population	Unique
Table 14.3.2.3.1 Urinaly Change	Urinalysis Parameters: Continuous Results and Change from Baseline to End of Treatment	Safety Population	Repeat
Table 14.3.2.3.2 Urinaly	Urinalysis Parameters: Categorical Results	Safety Population	Repeat
Table 14.3.2.3.3 Shift frequencies Urinaly Urinaly	Shift from Baseline to End of Treatment in Urinalysis Parameters	Safety Population	Repeat
Table 14.3.2.3.4 Potentia Urinaly Urinaly	Potentially Clinically Significant Results in Urinalysis values	Safety Population	Unique
Table 14.3.3.1 Vital Si	Vital Signs: Results and Change from Baseline	Safety Population	Repeat
Table 14.3.3.2 Potentia Signs Signs	Potentially Clinically Significant Results in Vital Signs	Safety Population	Unique
Table 14.3.4.112-LeadBaseline	12-Lead ECG Exam: Results and Change from Baseline	Safety Population	Repeat
Table 14.3.4.2 ECG In	ECG Interpretation in 12-Lead ECG Exam	Safety Population	Repeat

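### SAP Table 4 sets no limit for respiratory rate or SpO2, so the planned table of potentially clinically significant vital signs will hold no patient count for either

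*SAP*

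**What the plan says.** SAP 9.5 names systolic and diastolic BP and then "heart rate, respiration rate, pulse oximetry, and temperature will be listed for individual patients". It says that vital signs and changes from baseline are summarized by time point and that vital-sign outcomes are assessed for potential clinical significance. On the patient count it says: "The number and percent of patients with potentially clinically significant (PCS) values during the treatment phase will be summarized". The focus is on new-onset values, so a patient who already had a PCS value before treatment is not counted as new. For the definition of PCS it says: "The criteria for identifying potentially clinically significant vital signs values are provided in Table 4". Table 4 then has three rows: systolic BP, diastolic BP and heart rate.

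The output is Table 14.3.3.2, "Potentially Clinically Significant Results in Vital Signs", in the Safety Population (SAP 14.1.1). Protocol 12.10.4 says vital-sign outcomes are assessed for clinical significance and mentions SpO2 by name. SAP section 12 describes the SAP as consistent with the protocol apart from clarifications and minor modifications, and does not mention leaving any vital sign out.

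**The concern.** Safety is the primary objective, and the study drug has opioid activity. The protocol introduction names opiate-induced respiratory depression as an effect worth preventing in this setting, and section 4.1 states that tramadol is not associated with the side effects typical of stronger opioids. Respiratory rate and SpO2 are the two vital signs closest to that question. They are taken at the same times as BP and heart rate, yet only BP and heart rate receive a threshold-based count of patients.

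At stake is a simple descriptive number: how many treated patients had a low respiratory rate or a low SpO2 while on treatment. If someone asks for it after database lock, SAP section 1 requires it to be labelled post hoc. In an open-label study the limit would then have been chosen with the data in view.

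**Working it through.** **1. Coverage.** The parameters listed in SAP 9.5, set against Table 4:

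| Vital sign | Low limit | High limit |
|---|---|---|
| Systolic BP | <86 mm Hg, or fall ≥25 | >200 mm Hg, or rise ≥25 |
| Diastolic BP | <48 mm Hg, or fall ≥20 | >110 mm Hg, or rise ≥20 |
| Heart rate | <45 bpm, or fall ≥25 | >105 bpm with rise ≥25, or >125 bpm |
| Respiration rate | none | none |
| SpO2 | none | none |
| Temperature | none | none |

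Three of six have a limit. No other analysis section supplies one for the remaining three; the ECG criteria in SAP Table 5 repeat heart rate only. The only respiratory-rate and SpO2 figures in the documents are in protocol 7.2.1, criterion 4. They are an exclusion applied before the first dose, and the SAP does not carry them into the analysis.

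**2. The plan's own figure.** The one design figure is in SAP 2.7: about 90% probability of at least one event with true incidence 1% in 250 patients. 1 − 0.99^250 = 0.919, so it reproduces. This point does not depend on it.

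**3. Can the planned summaries stand in for a patient count?**

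Inputs:
- Vital signs at 0, 0.5, 1, 2, 3 and 4 h, then every 4 h in the first 48 h (protocol 6.6.4). Post-baseline times to 24 h are 0.5, 1, 2, 3, 4, 8, 12, 16, 20 and 24, so T = 10.
- Statistics at each time point: n, mean, SD, median, minimum and maximum (SAP section 3), for observed values and change from baseline (SAP 9.5).
- N = 250 (SAP 2.7), with N = 200 as an assumed lower value.
- Assumed readings: every SpO2 is 97% except one reading of 86% at each of the 10 times; all baselines are equal.

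Case A: the same patient is low at all 10 times. Case B: a different patient is low each time.

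With one value lower than the other N − 1 by d = 97 − 86 = 11, the mean is 97 − d/N and the SD is d/√N.
- N = 250: mean 97 − 11/250 = 96.956; SD 11/√250 = 0.696; median 97, minimum 86, maximum 97.
- N = 200: mean 97 − 11/200 = 96.945; SD 11/√200 = 0.778; same median, minimum and maximum.

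These values hold at all 10 times in both cases. With equal baselines, the change-from-baseline statistics are also the same in both.

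Patients with any low reading:
- Case A: 1/250 = 0.4%, or 1/200 = 0.5%.
- Case B: 10/250 = 4.0%, or 10/200 = 5.0%.

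**4. How far this generalizes.** Exchanging readings between two patients measured at the same time leaves every observed-value statistic unchanged at that time. For change from baseline this is assured only when the two baselines are equal. Otherwise the mean stays the same, but the SD, median, minimum and maximum can move. In the observed-value summaries, k low readings at each of T times are compatible with anything from k to k × T patients, provided that many patients were measured.

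**The case against.** The strongest reply is that nothing in the SAP is broken. The sentence on PCS counts names no parameter, Table 4 defines PCS, and Table 14.3.3.2 can be produced exactly as specified. That is correct. A reader might infer that the SAP commits to a respiratory-rate and SpO2 count and then fails to deliver it; the text does not go that far. Protocol 12.10.4 likewise promises an assessment of clinical significance, not a threshold count. What stands is that the assessment is stated for vital-sign outcomes without restriction, and the narrower scope of the count is not explained.

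A reader might also take SAP Table 3 as proof of oversight, because it writes NA where a limit is not set. It does not show that. NA there marks one unset side of a listed test; all 35 rows (10 hematology, 18 chemistry, 7 urinalysis) have at least one limit. Table 3 also has no row for magnesium, although magnesium is an eligibility test. A missing row is therefore not peculiar to Table 4.

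The information is not hidden either. The minimum would show a low value at each affected time, Listing 16.2.24 identifies the patients, and the adverse event tables count a patient once per preferred term. The last of these is a count of distinct patients, but it depends on what the investigator judges to be an adverse event (protocol 11.2.1.1), not on a common threshold.

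Finally, a count would not be a direct test of tramadol's respiratory effect. The study is uncontrolled, the synopsis places no restriction on narcotics or sedatives at surgery, and the documents do not say that oxygen use is recorded with each reading.

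**Conclusion.** The gap is real and should be closed. Followed to the letter, the plan gives no patient count for low respiratory rate or SpO2 in Table 14.3.3.2, and the by-time-point summaries cannot recover one. Three of the six listed vital signs are without a limit; temperature is the third.

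The tenfold difference (0.4% against 4.0% at N = 250) is a constructed extreme that shows what the summaries cannot distinguish. It is not an expected rate, and it assumes equal baselines. The conclusion also assumes that Table 4 is complete as it stands: the heart-rate row is followed by the footnote and then section 9.6, which makes lost rows unlikely, but the source PDF should be checked.

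This is a gap in descriptive coverage, not an error in a result. The documents do not support saying that these two parameters go unanalyzed.

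A reader might also take the QTcF summary in SAP 9.7 as a model for a new-onset count. It is not one: it uses the highest value at any time on treatment and is not limited to new onset. The rule that fits is the one already in SAP 9.5.

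**What to change.** Before database lock:

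- Add respiratory-rate and SpO2 rows to SAP Table 4 as analysis flags only, with limits chosen and dated by the sponsor. The pre-dose exclusion figures in protocol 7.2.1 should not be carried over by default; the SpO2 figure there is tied to supplemental oxygen.
- Report in Table 14.3.3.2 the number and percent of patients with PCS values during the treatment phase, with new-onset values shown, under the SAP 9.5 rule for BP and heart rate.
- State that the SpO2 flag applies regardless of supplemental oxygen, unless oxygen status was recorded, and that it is read descriptively because the study is uncontrolled.
- If temperature is meant to have no PCS limit, say so in 9.5.

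SAP section 3 keeps unscheduled measurements out of analyses, so the new rows would count scheduled readings only; a table footnote should say this.

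The cost is two pre-specified threshold choices and a little more programming for an output already planned. No new data are needed unless the SpO2 flag is made to depend on oxygen status.
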